##### ***Responder analyses for SRS, BFI scale - Item 3, BPI scale - Item 3 and FACIT-Dyspnea symptom score***

Thresholds for meaningful within-patient improvement on the SRS, BFI scale - Item 3, BPI scale - Item 3, and FACIT-Dyspnea symptom score were calculated using blinded data from

the DFI12712 study (methods described in PRO Psychometric Statistical Analysis Plan). The primary and secondary improvement thresholds for each measure are as follows:

- SRS: Primary threshold is change from baseline at Week 52  $\leq -12.5$  points; Secondary threshold is change from baseline at Week 52  $\leq -18$  points.
- BFI scale - Item 3: Primary threshold is change from baseline at Week 52  $\leq -1.7$  points; Secondary threshold is change from baseline at Week 52  $\leq -2.5$  points.
- BPI scale - Item 3: Primary threshold is change from baseline at Week 52  $\leq -2.5$  points; Secondary threshold is change from baseline at Week 52  $\leq -4.0$  points.
- FACIT-Dyspnea symptom score: Primary threshold is change from baseline at Week 52  $\leq -7.0$  points; Secondary threshold is change from baseline at Week 52  $\leq -5.6$  points.

Responder analyses will be conducted using these thresholds. For each measure, patients who meet or exceed the meaningful change threshold at Week 52 will be considered a responder and those who do not meet or exceed the threshold will be considered non-responders. For patients who have missing data at Week 52, they will be considered as non-responder. Separate responder analyses will be conducted using the primary and secondary thresholds for each measure.

Cumulative distribution functions (CDFs) will be generated by treatment group for SRS, BFI scale - Item 3, BPI scale - Item 3 and FACIT-Dyspnea symptom score. The CDFs will show the cumulative percent of patients on the y-axis and change from baseline to Week 52 scores on the x-axis. The CDFs will allow a visual inspection of the cumulative proportion of patients in each treatment group who achieved various levels of change on the PRO measure at Week 52.

#### **2.4.5.6 Compliance of eDiary data during PAP**

In addition, to assess the compliance for eDiary data including SRS, BFI scale - Item 3, and BPI scale - Item 3, the following summaries will be provided for each treatment group.

- The number and percentage of patient with  $\geq 4$  days of non-missing diary entries at each baseline and post-baseline collection visits up to Week 52 separately.
- The number and percentage of patient with  $\geq 4$  days of non-missing diary entries at both baseline and Week 52.
- The number and percentage of patient with  $\geq 4$  days of non-missing diary entries at baseline and all scheduled post-baseline visits up to Week 52.

Compliance on the FACIT-Dyspnea symptom score will be calculated as (a) the number and percentage of patients who have non-missing values at baseline and each post-baseline visits up to Week 52 separately, (b) the number and percentage of patients who have non-missing values at both baseline and Week 52, and (c) the number and percentage of patients who have non-missing values at baseline and all scheduled post-baseline visits up to Week 52.

#### **2.4.5.7 Additional efficacy analyses in PAP**

No multiplicity adjustment will be conducted for additional efficacy endpoints. Nominal p-values will be reported in the tables. No sensitivity analyses will be performed for the additional efficacy

endpoints. All of the analyses specified below will be done in mITT population using data obtained before initiation of rescue therapy.

### ***Liver function tests***

The percentage change in ALT, AST, direct bilirubin, and total bilirubin from baseline up to Week 52 at pre-infusion time point will be analyzed using MMRM model described in [Section 2.4.5.1](#). Data collected at quarterly visits will be included in the MMRM model.

### ***Pulmonary function tests***

The percentage change in FEV1 (% predicted), FVC (% predicted) and TLC (% predicted) from baseline up to Week 52 will be analyzed using the MMRM model described in [Section 2.4.5.1](#).

### ***Pulmonary imaging - HRCT***

A qualitative assessment will be made for the following features: interstitial lung disease (reticular pattern), ground glass appearance, reticulo-nodular density (nodular densities) and pleural thickening of the right and left lungs based on a scale 0-3, as explained in [Section 2.1.4.3](#).

The change in the two types of mean scores for each feature from baseline up to Week 52 will be analyzed using the MMRM model described in [Section 2.4.5.1](#).

### ***Pulmonary function imaging – chest X-ray***

The lung features (interstitial (overall ILD), reticular, nodular, consolidation and pleura) will be scored subjectively for the degree of diffuse lung disease (infiltrative lung disease) in a scale of 0-3 for each side of lungs, as explained in [Section 2.1.4.3](#).

For chest x-ray imaging, interstitial provides an overall assessment of interstitial lung disease with reticular and nodular may provide more supportive information on type of interstitial involvement. Consolidation provides a measure of air space disease and is assessed in addition to interstitial involvement. As HRCT provides a more robust characterization of the diffuse lung disease, only interstitial (overall ILD) of the chest X-ray will be analyzed; however data for all features will be provided in data listings.

The change in mean scores across two lungs for interstitial, which provides a measure of overall interstitial involvement, from baseline up to Week 52 will be analyzed using the MMRM model described in [Section 2.4.5.1](#).

### ***Treadmill ergometry***

The parameters of cycle ergometry assessments are noted in [Section 2.1.4.3](#). The change in percent predicted values (or observed values if the percent predicted value is not available) from baseline up to Week 52 will be analyzed using the MMRM model described in [Section 2.4.5.1](#).

### ***Fasting lipids (including lipoproteins of interest)***

The percentage change from baseline up to Week 52 values will be analyzed using MMRM model described in [Section 2.4.5.1](#). Summary plots of the LS means from the MMRM of the change from baseline up to Week 52 with 95% CIs will be provided.

### ***Hematology***

Platelet and hemoglobin are efficacy parameters. Baseline definitions of hematology parameters are defined in [Section 2.6.1](#). In the visits where two samples are to be collected, the average of two results will be used for summary and plots. Analysis of platelets has already been described under secondary efficacy parameters. For hemoglobin, the MMRM model as used in the primary analysis of spleen volume under primary efficacy endpoints will be used to compare treatment groups for percentage change from baseline up to Week 52, using mITT population. Data collected at quarterly visits will be included in the MMRM model.

### ***Bone disease assessments***

#### **Bone marrow burden**

The change from baseline to the last observation during PAP will be analyzed using ANCOVA including covariates of baseline and treatment for total BMB score, femur score and spine score separately.

#### **DXA parameters**

The change from baseline to the last observation during PAP will be analyzed using ANCOVA model including covariates of baseline and treatment for BMD, T-score and Z-score by the region of femur and spine separately.

#### ***Bone biomarkers***

Bone-specific alkaline phosphatase and C-telopeptide are bone biomarkers. The change from baseline to Week 52 for these bone biomarkers will be analyzed using MMRM model described in [Section 2.4.5.1](#).

#### ***Efficacy biomarkers***

Normalized values of serum chitotriosidase, and results from ligand 18 (CCL-18), and angiotensin-converting enzyme (ACE) are efficacy biomarkers. The percentage change from baseline up to Week 52 for efficacy biomarkers will be analyzed using MMRM model described in [Section 2.4.5.1](#).

### ***Physician's global assessment***

At the scheduled post-baseline visits, the investigator will also evaluate the patient's current clinical status compared to screening (baseline) by marking 1 of 7 categories and those 7 categories will be converted to numeric values as follows:

- "Marked improvement of daily activities" = 3.
- "Moderate improvement of daily activities" = 2.
- "Mild improvement of daily activities" = 1.
- "No change" = 0.
- "Mild worsening of daily activities" = -1.
- "Moderate worsening of daily activities" = -2.
- "Marked worsening of daily activities" = -3.

Observed numeric values at each post-baseline visits will be analyzed using MMRM model described in [Section 2.4.5.1](#). And in the MMRM model, the baseline value will be Physician's global assessment of severity at screening with value of 1=mild, 2=moderate, 3=severe.

In addition, as supportive analysis, at Week 52, patients will be categorized as responder if having numeric value of 3, 2, or 1, otherwise, patient will be categorized as non-responder if having numeric value of 0, -1, -2, -3 or missing. This binary measure of responder (yes vs no) at Week 52 will be analyzed with logistic regression including treatment group and baseline as covariates.

### ***NMR of HDL***

The NMR of HDL data will be provided in data listings.

### ***Liver function via echo-Doppler ultrasound***

A frequency shift table for detected signs of portal vein hyperpressure will be provided.

### **2.4.5.8 PAP+ETP efficacy analyses**

All of the efficacy endpoints throughout the study treatment epoch including all longitudinal time points from both PAP and ETP will be summarized by randomized treatment groups in PAP, using mITT population and the same baseline definition for both randomized treatment groups (latest observation prior to the first infusion of the IMP in the study, see [Section 2.6.1](#) for the details of hematology parameters and possibly ECG parameters). ANCOVA model with baseline and treatment group as covariates will be used to assess the means of each treatment group and the 95% CIs of both treatment groups as well as the difference between two groups at each time point. It is understood that all patients in ETP are on olipudase alfa. Summary plots and by-patient plots will be provided as appropriate.

For the primary efficacy endpoints, in addition to the above summaries, the descriptive summaries over time while patients are treated with olipudase alfa using mITT population will be provided.

Since patients who were randomized to placebo group start receiving olipudase alfa when they enter the ETP, their baseline will be defined as the latest observation prior to the first infusion of olipudase alfa.

#### **2.4.6 Analyses of safety data**

The summary of safety results will be presented by actual treatment received using safety population. The epochs for safety analysis have been defined in [Section 2.1.5](#). The assessment of safety measures [REDACTED] will be conducted through pooled analyses and presented in the integrated summary of safety (ISS).

##### ***General common rules***

All safety analyses will be performed on the safety population as defined in [Section 2.3.2](#), unless otherwise specified, using the following common rules:

- The baseline value is defined as the last available value before the first infusion of the study drug, except for hematology parameters and possibly ECG parameters. For complete definition of baseline, refer to [Section 2.6.1](#).
- The analysis of the safety variables will be essentially descriptive and no systematic testing is planned.

The potentially clinically significant abnormality (PCSA) values are defined by the Sponsor according to predefined criteria/thresholds based on literature review for clinical laboratory tests, vital signs, and ECG; this list is provided in [Section 7.2](#).

- PCSA criteria will determine which patients had at least 1 PCSA during the treatment-emergent adverse event period, taking into account all evaluations performed during the treatment-emergent adverse event period, including unscheduled or repeated evaluations. The number of all patients with any post-baseline evaluation will be the numerator for the on-treatment PCSA percentage.
- The treatment-emergent PCSA denominator by group for a given parameter will be based on the number of patients assessed for that given parameter in the treatment-emergent adverse event period by treatment group on the safety population.
- Before determining a value as PCSA, the value will be rounded to the precision that the PCSA criterion is defined.

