11.5.5 Analyses of safety data

Safety analyses will be performed using the safety population by the actual treatment received, irrespective of the treatment to which the patient has been randomized. The actual treatment received is defined as:

- PAP analysis: olipudase alfa if any infusion in the PAP contains olipudase alfa (including any rescued placebo patient); placebo if all infusions in the PAP contain only placebo
- ETP analysis: olipudase alfa

Additional summaries may be conducted using the most recent dose the patient received before the event of interest.

The summary of safety results will be presented by treatment arm. All safety analyses will be performed using the following common rules:

- The baseline value is defined generally as the last available value before randomization, except hematology and ECG parameters. Baseline for hematology parameters is derived as the mean of all available results before the start of first infusion. Baseline for ECG parameters is derived as the mean of all available results on the Day 1/Week 0 visit before the start of first infusion.
- The following definitions will be applied to laboratory parameters, ECGs and vital signs.
 - The potentially clinically significant abnormality (PCSA) values are defined as abnormal values considered medically important by the sponsor according to predefined criteria/thresholds based on literature review and defined by the sponsor for clinical laboratory tests and vital signs.
 - The PCSA criteria will determine which patients had at least 1 PCSA during the on-treatment period, taking into account all evaluations performed during the on-treatment period, including unscheduled or repeated evaluations. The number of all such patients will be the numerator for the on-treatment PCSA percentage.

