### **2.4.6.2 Laboratory data**

For parameters that are reported as below the quantification limit (BQL), the results often convey a clinically meaningful change. Therefore, a numerical value is necessary to be imputed for including these in descriptive statistics calculations. For all these parameters either the lower limit of quantification (LLOQ) is available in the database, or the result is reported as <xx. The numeric value for results of BQL will be imputed as LLOQ/2; the numeric value for results reported as <xx will be imputed as xx/2.

In hematology, platelets and hemoglobin are part of efficacy parameters, and have been described under [Section 2.1.4](#). For the rest of hematology parameters, the baseline will be defined the same way ([Section 2.6.1](#)), and any visit which is scheduled to collect two samples pre-infusion for WBC, the average of the two values will be used as pre-infusion value.

Observed values, change from baseline and percent change from baseline to scheduled study time points will be summarized in separate groups of hematology (excluding hemoglobin and platelets which are considered efficacy parameter, hence the analyses have been described in [Section 2.4.5](#)), liver function tests, coagulation, etc. as described in [Section 2.1.5](#) (excluding lipids which have been described as part of efficacy, [Section 2.4.5.7](#)). Summary plots over time will also be provided as needed.

Laboratory values will be classified as normal, above normal, or below normal based on normal ranges when provided by the laboratory. Shifts from baseline to scheduled time points, any time during the on-treatment period and the last available value, in the abnormality of any parameters will be provided.

PCSA values for clinical chemistry, hematology and liver function tests (provided in [Section 7.2](#)) during the study (from first infusion to last available observation) will be summarized. PCSA values for hematology, liver function test and clinical chemistry parameters will be provided in separate listings.

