#### **2.4.6.3 Vital signs**

Vital signs will include heart rate (HR, beats/minute), systolic and diastolic blood pressure (SBP/DBP, mmHg), respiratory rate and body temperature (°F or °C). Each vital sign parameter will be summarized as observed parameter value and change from baseline at each scheduled time point.

PCSA values (provided in [Section 7.2](#)) during the study (from first infusion start to last available observation) will be summarized.

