#### **2.4.6.4 Electrocardiogram variables**

For ECG parameters, the baseline is defined in [Section 2.6.1](#). The observed data and change from baseline will be summarized at each scheduled time point.

PCSA values (provided in [Section 7.2](#)) will be summarized during the study (from first infusion start to last available observation).

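### SAP 2.4.6 puts every evaluated patient in the PCSA numerator, so the percentage would read about 100% in each arm; the grouping of a rescued placebo patient also needs one stated rule

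*SAP*

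**What the plan says.** **PCSA percentage.** The general common rules in SAP 2.4.6 begin with the purpose: "PCSA criteria will determine which patients had at least 1 PCSA during the treatment-emergent adverse event period". The next sentence sets the numerator: "The number of all patients with any post-baseline evaluation will be the numerator for the on-treatment PCSA percentage". The following bullet sets the denominator: "The treatment-emergent PCSA denominator by group for a given parameter will be based on the number of patients assessed for that given parameter", by treatment group in the safety population. Protocol 11.5.5 has the parallel rule. After describing patients with at least one PCSA, it says: "The number of all such patients will be the numerator for the on-treatment PCSA percentage". SAP 1.5, which lists departures from the protocol's statistical section, does not mention this one.

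The rule feeds the PCSA summaries in SAP 2.4.6.2 (laboratory), 2.4.6.3 (vital signs) and 2.4.6.4 (ECG). For laboratory data the SAP adds: "PCSA values for hematology, liver function test and clinical chemistry parameters will be provided in separate listings". For vital signs it says only that PCSA values "during the study (from first infusion start to last available observation) will be summarized", with equivalent wording for ECG and no PCSA listing for either.

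**Grouping of safety data.**
- By randomized arm: SAP 2.4 (summaries in general) and SAP 2.4.6.1 item 1 (adverse events starting in the PAP).
- By actual treatment: SAP 2.3.2, the opening of SAP 2.4.6, and protocol 11.5.5, which classes a patient as "olipudase alfa if any infusion in the PAP contains olipudase alfa (including any rescued placebo patient".
- The adverse event denominator in SAP 2.4.6.1 (Generalities) is the safety population, which SAP 2.3.2 groups by treatment actually received.
- SAP 2.3.2, 2.4.6.1.1 and 2.4.6.1.5 present post-rescue data separately.
- SAP 2.4.6.14 counts only ETP exposure for patients randomized to placebo, with a baseline before the first ETP infusion. SAP 2.4.6.1 item 2 counts events on olipudase alfa in either period.

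**The concern.** A PCSA percentage should say how many of the patients assessed for a parameter crossed its threshold. As worded, the SAP divides evaluated patients by assessed patients. That measures data availability, and it gives the same answer for a parameter with no abnormal values as for one where every patient is abnormal. Confirming safety is a secondary objective, and the comparison is descriptive, in small arms. A table that cannot separate the arms does not serve that objective.

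The grouping question is narrower. If a placebo patient is rescued in the PAP, one section keeps that patient's adverse events under placebo while others count the patient under olipudase alfa. A numerator taken from SAP 2.4.6.1 item 1 and a denominator taken from the safety population would then describe different groups. In the PAP+ETP tables, SAP 2.4.6.14 would omit that patient's olipudase alfa exposure during the PAP and take as baseline a value recorded after that exposure had begun.

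**Working it through.** The documents state no PCSA percentage, so there is no figure to reproduce. PCSA counts and rescue counts below are assumptions. Arm size comes from SAP 1.4: about 36 patients randomized 1:1, so 36/2 = 18 per arm.

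**Step 1: the rule as written.** Let E be patients in an arm evaluated at least once after baseline, A those assessed for the parameter in the treatment-emergent period, and k those with at least one PCSA.

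As written: 100 × E/A. The count k does not appear. Anyone in A is also in E, so within an arm the result cannot fall below 100%.
- E = 18, A = 18: 18/18 = 100%.
- E = 18, A = 17 (one patient lacks the parameter): 18/17 = 105.9%.

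**Step 2: the protocol rule.** 100 × k/A, with A = 18:

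| k (assumed) | Protocol 11.5.5 | SAP 2.4.6 as written |
|---|---|---|
| 0 | 0% | 100% |
| 1 | 5.6% | 100% |
| 2 | 11.1% | 100% |
| 5 | 27.8% | 100% |
| 9 | 50.0% | 100% |

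An assumed contrast of 6/18 against 1/18 is 5/18 = 27.8 points. As written it would print as 100% against 100%, a difference of 0.

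**Step 3: which wording is intended.** The sentence just before the numerator in SAP 2.4.6 identifies patients with at least one PCSA. The protocol follows the same sentence with a numerator of those patients. SAP 1.5 records no change. All three point to k. SAP 1.5 refers to protocol version 11 and the protocol supplied is version 15, but the later amendments' summaries of changes list no edit to this wording.

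**Step 4: rescue, under stated assumptions.** The documents give no rescue rate. Assume r placebo patients are rescued in the PAP, each with one event before rescue, and nobody else has that event. Differences are olipudase alfa minus placebo, in percentage points.

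| r | Randomized arm | Actual treatment | Randomized numerator, actual denominator |
|---|---|---|---|
| 0 | no effect | no effect | no effect |
| 1 | 0/18 − 1/18 = −5.6 | 1/19 − 0/17 = +5.3 | 0/19 − 1/17 = −5.9 |
| 2 | 0/18 − 2/18 = −11.1 | 2/20 − 0/16 = +10.0 | 0/20 − 2/16 = −12.5 |

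Under this deliberately extreme assumption the sign depends on the grouping. The last column is what a literal combination of SAP 2.4.6.1 item 1 and its denominator gives.

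**The case against.** The intent is plain. A table showing 100% everywhere, or 105.9%, would fail any check on sight, so a programmer would probably use the right numerator. The sentence also does not stand alone. SAP 2.4.6.2 gives PCSA listings for hematology, liver tests and chemistry, plus shift tables. SAP 2.4.6.3 and 2.4.6.4 summarize observed values and changes at each scheduled time point. Protocol 11.5.5.2 calls for outlier summaries of ECG and vital signs, and 11.5.5.3 for frequencies of clinically significant laboratory abnormalities; SAP 1.5 withdraws neither. All of this stands and limits the consequence. It does not make the sentence right: it is the only PCSA numerator the SAP states.

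A reader might infer that ECG and vital-sign abnormalities would go unreported because no PCSA listing is stated for them. The summaries just named do not support that.

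On rescue, it is fair to say that SAP 2.4.6.1 item 1 can be read as a specific rule for adverse events, that SAP 2.4.6 can be read as overriding the general statement in SAP 2.4, and that separate reporting of post-rescue data suggests its removal from the main tables. But the denominator in SAP 2.4.6.1 still points to actual treatment, and no section says that post-rescue data are removed.

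**Conclusion.** The PCSA numerator in SAP 2.4.6 is wrong as written. Followed literally, it gives at least 100% in each arm for any parameter, whatever the data. It is a drafting error in a descriptive rule: no hypothesis test or error rate is touched, and other planned outputs would still show the abnormal values. The 18-per-arm figures assume the planned size and 1:1 split.

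The grouping inconsistency is real but conditional. It has no effect unless a placebo patient is rescued in the PAP, and the figures for one and two rescues are illustrations only. Three stronger readings are tempting and not supported:
- That the SAP has no rule for a rescued placebo patient. SAP 2.3.2 and protocol 11.5.5 both state one; the trouble is that other sections do not follow it.
- That aligning everything to actual treatment would settle which treatment an event belongs to. It would make the tables consistent, but an event before rescue would still sit in the olipudase alfa column. That follows from a prespecified rule and is separate from the inconsistency.
- That a platelet fall meeting the rescue criterion must also count as a PCSA. The PCSA criterion depends on change from a baseline that averages all available pre-infusion values (SAP 2.6.1), including unscheduled ones (SAP 2.6.4), so the documents do not guarantee it.

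**What to change.** 1. In SAP 2.4.6, general common rules, replace the numerator sentence with: *The number of patients with at least 1 PCSA for that parameter during the treatment-emergent adverse event period, by treatment group and among patients in the denominator, will be the numerator.*
2. Reconcile SAP 2.3.2, 2.4, 2.4.6, 2.4.6.1 (items 1 and 2, and the denominator under Generalities) and 2.4.6.14 to one stated grouping for safety tables. If randomized grouping is kept for PAP adverse events, say so, match the denominator, and list the departure from protocol 11.5.5 in SAP 1.5. Presentation by treatment at onset is an option if the sponsor wants events before rescue shown under placebo.
3. State whether post-rescue data presented separately under SAP 2.3.2, 2.4.6.1.1 and 2.4.6.1.5 are excluded from the main PAP tables.
4. In SAP 2.4.6.14, start the previous-placebo group, and set its baseline, at the first olipudase alfa infusion in either period, as SAP 2.4.6.12 already does for the anti-drug antibody baseline.

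The cost is a few sentences of SAP text, with no new data and no protocol amendment.
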